3.4.2 Exposure/Independent Variables of Interest

For eligible patients, use of dapagliflozin will be defined by the date of first dapagliflozin prescription in the database.

3.4.3 Other Co-variates/Control Variables

Not applicable.

4 STATISTICAL ANALYSIS

4.1 Statistical Analysis Methods

The details of the data analysis will be documented in a Statistical Analysis Plan (SAP) document, which will be finalized before the first extraction of data from the databases. The SAP will elaborate on the analytic plans outlined in the protocol; any major modifications will be reflected in a protocol amendment.

The goal of the analyses is to describe the characteristics of patients who use dapagliflozin.

Since the study is purely descriptive, missing data will not be imputed but the amount of missing data will be reported for each variable.

^[2] eGFR will be estimated by the creatinine clearance calculated by means of the Cockroft & Gault formula if it is not available in the data base.

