1.2 Research Question

Research question 1: What are the baseline characteristics of the patients prescribed dapagliflozin in Europe?

Research question 2: What proportion of patients prescribed dapagliflozin have baseline moderate to severe renal impairment?

Research question 3: What proportion of patients prescribed dapagliflozin are 75 years of age or older at the time of the index prescription?

Research question 4: What proportion of patients prescribed dapagliflozin are also users of loop diuretics or pioglitazone during the baseline period and the available follow-up period?

Research Question 5: What proportion of patients prescribed dapagliflozin does not have a diagnosis of Type II Diabetes during the baseline period or on the index date?

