Number of patients with BMI recorded (3 years history + calc)	40,0%	62,7%	54,0%	32,1%	77,5%	24,4%
Number of patients with waist recorded (1 year history)	1,2%		0,4%			
Number of patients with Blood Pressure recorded (1 year history)	64,8%	54,5%	91,6%	28,2%	40,9%	73,4%
average records by year by patient	3,34	2,73	2,80	5,72	2,44	4,4
BIOLOGICAL EXAMS	500 800		- 20			
Number of patients with a fasting blood glucose test	29,5%	67,7%	45,6%	54,5%	44,1%	68,5%
Number of patients with a Hba1c rate	43,2%	66,4%	88,0%	77,1%	27,5%	53,6%
Number of patients with Total cholesterol	26,7%	61,2%	83,8%	57,2%	0,0%	56,4%
Number of patients with LDL	26,8%	55,4%	55,9%	54,1%	26,5%	53,1%
Number of patients with HD L	26,0%	58,3%	74,7%	52,8%	27,7%	55,9%
Number of patients with Triglycerid	27.2%	60,3%	63,9%	56,6%	41,8%	56,1%

Table 3.3.2-3: Information collected on serum creatinine and eGFR for T2DM patients in Cegedim LPDs during the course of one year (year 2012)

	FRAN	NCE	GERM	ANY	ITA	LY	SPA	IN	BELG	IUM	UK	
Number of patients in the panel	1 800	000	620 (000	700 (000	130	000	360 (000	3 200	000
T2DM patients (% of panel population)	65 000	4%	37 000 6% 42 000 6%		14 000 11%		13 000	4%	118 000	4%		
T2DM patients:												
with creatinine values recorded	20 500	32%	26 600	72%	25 000	60%	5 700	41%	7 350	57%	105 000	89%
with eGFR values recorded or calculated*	12 300	20%	19 300	52%	20 850	50%	4 200	30%	1 100	9%	93 300	79%

^{*}eGFR estimated using the Cockcroft-Gault (Appendix 5) or MDRD estimation formula (Appendix 4)

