3.4.1 Outcomes/Endpoint Variables

Table 3.4.1-1 includes the characteristics and definitions of how dapagliflozin users will be categorized and described.

Table 3.4.1-1: Categorization of Dapagliflozin Users

Characteristic	Definition
Patient Demographics, at initiation of dapagliflozin use:	
Age categories	< 45, 45-59, 60-74, >= 75
Sex	Male or Female
Country	Belgium, France, Germany, Italy, Spain, United Kingdom
Concomitant medications before, at initiation of and	Loop diuretics (ATC code C03Cx)
during dapagliflozin use 1	Pioglitazone (Actos, Glustin) (ATC code A10BG),
	Biguanides (ATC Code A10BA)
	Sulfonamide derivates (ATC code A10BB and A10BC)
	Dipeptidyl peptidase 4 inhibitors (DDP4) (ATC code A10BH)
	Glucagon-like peptide 1 (GLP-1, exenatide, liraglutide, ATC code A10BX),
	Alpha glucosidase inhibitors (ATC code A10BF).
	Insulin (ATC code A10A)
Concomitant co-morbidities, at initiation of dapagliflozin use:	
Baseline history of moderate renal impairment	CrCl or eGFR ² value between 30-60 within 12 months prior to the dapagliflozin dispensing
Baseline history of severe renal impairment	CrCl or eGFR value < 30 within 12 months prior to the dapagliflozin dispensing
Baseline history of renal failure	Diagnosis codes for end stage renal disease or dialysis (see Appendix 3)
Congestive heart failure	Diagnosis codes for congestive heart failure (see Appendix 3)
Hypertension	Diagnosis codes for hypertension (see Appendix 3)
Type 2 Diabetes Mellitus, at initiation of dapagliflozin use:	Diagnostic code for T2DM within 12 months prior to the dapagliflozin dispensing (see Appendix 3) OR
	Prescription for an antiglycemic medication within 12 months prior to the dapagliflozin dispensing

Table 3.4.1-1: Categorization of Dapagliflozin Users

Characteristic	Definition
Dapagliflozin Dose, at initiation of dapagliflozin	10 mg
use:	5 mg
Off-Label Use	Patients meeting one of the following criteria:
	 17 years old or younger on index date
	• 75 years of age or older on index date
	 No diagnostic codes for Type 2 Diabetes Mellitus, at or before the initiation of dapagliflozin use (see definition above)
	• Baseline history of moderate renal impairment (see definition above)
	• Baseline history of severe renal impairment (see definition above)
	• Baseline history of renal failure (see definition above)

^[1] Pioglitazone sales are suspended in France and Germany

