4.1.1.1 Missing Data on Serum Creatinine and eGFR

In order to assess the risk of informative missingness the impact of missing key variables (e.g. BMI and eGFR) will be checked by describing patients with and without missing values respectively regarding basic characteristics available for all or most patients including age, gender, country of residence, co-medication and co-morbidity.

However, all analyses requiring information on serum creatinine and eGFR will be based primarily on information from the THIN database in the UK and from the German LPD database, which are the best documented.

Analyses will be performed also for the other countries covered by this study but the interpretation will take into account the loss of information. (See section 4.1.1.2: Sensitivity analysis.)

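### The renal-impairment proportion (research question 2) has no class for patients without a renal value, so over all initiators it is only a lower bound that moves with testing

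*Protocol*

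**What the plan says.** Protocol section 1.2, research question 2, asks: "What proportion of patients prescribed dapagliflozin have baseline moderate to severe renal impairment". The population named is everyone prescribed the drug, not everyone with a renal measurement.

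Table 3.4.1-1 (section 3.4.1) defines moderate impairment by a CrCl or eGFR "value between 30-60 within 12 months prior to the dapagliflozin dispensing" and severe impairment by "CrCl or eGFR value < 30 within 12 months prior to the dapagliflozin dispensing". Renal failure is a separate row, identified by diagnosis codes. The off-label composite in the same table takes patients who meet at least one listed criterion, including these three renal rows. None of these entries provides for a patient with no value.

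On missing data, section 4.1 states that "missing data will not be imputed but the amount of missing data will be reported for each variable". Section 4.1.1.1 adds a check, "describing patients with and without missing values respectively regarding basic characteristics available for all or most patients", and says that analyses needing creatinine or eGFR "will be based primarily on information from the THIN database in the UK and from the German LPD database". For the other countries it promises cautious interpretation and points to section 4.1.1.2. Section 3.3.2 permits, but does not require, a two-year look-back and a search for kidney-disease codes.

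**The concern.** The numerator needs a recorded value and the denominator does not. A patient with neither a value in the window nor a renal-failure code cannot enter the numerator but stays in the denominator. In the composite, the same patient falls outside off-label use unless age or a missing diabetes diagnosis brings them in. The proportion therefore depends on two things, how often impaired patients receive the drug and how often renal function is recorded, and the protocol's own table shows that recording differs greatly between countries.

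Use in renal impairment is one of the four uses the study is meant to describe, and section 1.1 says the study answers a regulatory request. A low figure could be taken as reassurance when it partly reflects absent laboratory entries. Countries with identical prescribing could appear to differ.

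**Working it through.** **Inputs.** Table 3.3.2-3 gives 2012 counts of T2DM patients, those "with creatinine values recorded" and those "with eGFR values recorded or calculated". The protocol does not give the prevalence of impairment in untested patients relative to tested ones. Call this ratio r; it is assumed here over 0 to 1.5.

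**Step 1: reproduce the coverage, f = patients with eGFR / T2DM patients.**

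| Country | Counts | f | Printed | Without eGFR, 1 − f |
|---|---|---|---|---|
| UK | 93,300 / 118,000 | 79.1% | 79% | 20.9% |
| Germany | 19,300 / 37,000 | 52.2% | 52% | 47.8% |
| Italy | 20,850 / 42,000 | 49.6% | 50% | 50.4% |
| Spain | 4,200 / 14,000 | 30.0% | 30% | 70.0% |
| France | 12,300 / 65,000 | 18.9% | 20% | 81.1% |
| Belgium | 1,100 / 13,000 | 8.5% | 9% | 91.5% |

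The printed figures reproduce, apart from a small mismatch for France that does not matter here. For Belgium, the printed 9% gives 91% without eGFR. UK and Germany pooled have 112,600 / 155,000 = 72.6% with an eGFR.

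**Step 2: size of the understatement.** Let p be the prevalence in tested patients.

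- All-initiator figure: f·p
- True figure: f·p + (1 − f)·r·p
- Relative understatement: (1 − f)·r / [f + (1 − f)·r]

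The prevalence p cancels. The result equals 1 − f only when r = 1. Example, UK at r = 0.5: 0.209 × 0.5 = 0.105, and 0.105 / (0.791 + 0.105) = 12%.

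| Country | r = 0 | r = 0.5 | r = 1 | r = 1.5 |
|---|---|---|---|---|
| UK | 0% | 12% | 21% | 28% |
| Germany | 0% | 31% | 48% | 58% |
| Belgium | 0% | 84% | 92% (91% from the printed 9%) | 94% |

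**Step 3: what a tested-only figure would do.** Its relative error is 1 / [f + (1 − f)·r] − 1. At r = 1 it is zero. At r = 0.5 it overstates by 12% (UK), 31% (Germany) and 84% (Belgium). At r = 1.5 it understates by 9% (UK) and 19% (Germany). Neither denominator is safe alone.

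**Step 4: width of the bounds.** With an illustrative p of 10%, the lower bound is f·p and the upper bound is f·p + (1 − f). For the UK this is 7.9% to 7.9% + 20.9% = 28.8%. For Germany it is 5.2% to 5.2% + 47.8% = about 53%.

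**Step 5: how far better derivation would help.** The Appendix 4 equation needs no weight. If eGFR were derived for everyone with a creatinine value, the share without a value would be 1 − 105,000/118,000 = 11% (UK), 1 − 26,600/37,000 = 28% (Germany) and 1 − 20,500/65,000 = 68% (France). The gap narrows but does not close.

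**The case against.** A reader might infer that the protocol instructs analysts to count untested patients as unimpaired. It does not. No sentence says so, and calling such a patient unimpaired would sit badly with a rule against imputation. The statistical analysis plan, which is not shown, may well add a missing row. This part of the objection stands: the problem is a literal consequence of the question and the definitions, not a stated rule.

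A reader might also quote an understatement of 21% to 91% without conditions. Those figures are only the shares of 2012 T2DM patients without an eGFR. They equal the understatement only if r = 1, and section 4.1.1.1 itself treats informative missingness as open. They describe all T2DM patients, not initiators. The top of the range is Belgium, where section 1.1 reports that reimbursement was not achieved; the same section expects no users from France. Diagnosis codes will also catch some untested patients with renal failure.

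The section 2.1 objective concerns impairment that is already known. For that target, known cases over all initiators is a legitimate proportion, and this stands too. But research question 2 and the composite do not carry that restriction, so the figure needs the label.

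The safeguards deserve credit but do not settle the matter. Reporting the amount missing and comparing patients with and without values describe the gap without changing the proportion. Making the UK and Germany primary still leaves 21% and 48% without an eGFR at 2012 rates. Section 4.1.1.2, the place referred to for the other countries, covers short enrolment and specialist prescribing and says nothing on missing renal values. Section 1.1 confines missing-data sensitivity analyses, for now, to discussion of the UK data.

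Leaving table layout to the analysis plan is normal. The research question, the case definitions and the composite, however, are fixed in the protocol, and they are what lack the class.

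**Conclusion.** The point holds in a limited form. As defined, the all-initiator proportion is one of known impairment. It is a lower bound on true impairment, and its distance from the truth depends on each country's testing. With 2012 T2DM coverage and equal prevalence in tested and untested patients, the understatement is about 21% (UK) to 48% (Germany) in the primary databases, and about 91% in Belgium, where few users may arise. At half the prevalence in untested patients it is 12% (UK) and 31% (Germany). It is smaller still if initiators are tested more often, and zero if no untested patient is impaired. The direction is downward for every r above zero; the size cannot be fixed from the protocol. The documents support neither a stated rule that untested patients are unimpaired nor an unconditional 21% to 91%.

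**What to change.** In Table 3.4.1-1 and in the off-label composite, classify renal status as impaired, not impaired or unknown. By country, report side by side:

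- (a) known impaired over all initiators, labelled as a lower bound;
- (b) impaired over initiators with a qualifying value, with renal-failure cases known only from a code shown separately and kept out of this denominator, since they would add positives without matching negatives;
- (c) an upper bound over all initiators, with every unknown counted as impaired.

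Use the same 12-month window in every country for these figures. Keep the two-year look-back and the diagnosis-code search of section 3.3.2 as a sensitivity analysis.

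The cost is some protocol and analysis-plan wording and a few more table rows. The tested-only figure in (b) may overstate if testing is selective, and the bounds will be wide where coverage is low; showing all three makes that visible.

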4.1.1 Analysis Plan for Primary Objective

Descriptive statistics will be calculated to describe baseline characteristics in dapagliflozin initiators. These characteristics include age group, sex, dapagliflozin dose, country, selected comorbidities, selected concomitant medications, frequency of laboratory testing, and available results of laboratory testing (see Table 3.4.1-1).

We will also describe dapagliflozin use within and outside (off-label use) the labeled indication of type 2 diabetes.

Categorical variables will be summarized by frequencies and proportions, and continuous variables will be summarized by means and standard deviations or medians and interquartile ranges. Because this is a descriptive drug utilization study, formal comparative tests of significance will not be performed.

4.1.1.1 Missing Data on Serum Creatinine and eGFR

In order to assess the risk of informative missingness the impact of missing key variables (e.g. BMI and eGFR) will be checked by describing patients with and without missing values respectively regarding basic characteristics available for all or most patients including age, gender, country of residence, co-medication and co-morbidity.

However, all analyses requiring information on serum creatinine and eGFR will be based primarily on information from the THIN database in the UK and from the German LPD database, which are the best documented.

Analyses will be performed also for the other countries covered by this study but the interpretation will take into account the loss of information. (See section 4.1.1.2: Sensitivity analysis.)

4.1.1.2 Sensitivity analysis

In order to assess the effect of excluding patients prescribed dapagliflozin but not included because of enrollment less than one year before index date, these patients will be counted and their main characteristics at index date (age, gender, eGFR) will be described together with the characteristics of patients included in the study.

To study patients that may be prescribed dapagliflozin in a specialist setting (such as patients with kidney disease and/or patients older than 75 years, paediatric patients), we will primarily use the UK THIN database in which references to a specialist are recorded.

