Study Population: All patients identified in the database(s) who newly received at least one dapagliflozin prescription during the study period. Dapagliflozin use will be representative of the uptake of dapagliflozin in the respective countries.

Data Collection Methods: Cegedim Strategic Data (CSD) Longitudinal Patient Databases (LPDs) come directly from physicians' EMR. Participating physicians use CSD-provided software to record their daily patient interactions and data are transmitted regularly to the Cegedim coordinating center where they are cleaned and de-identified.

Data Sources: CSD's LPDs include data from 5.8 million active patients. Over 4,000 general practitioners (GPs) in six European countries (Belgium, France, Germany, Italy, Spain and United Kingdom) are part of the LPD panels.

Patient metrics in the LPDs include Demographics (Year of birth, gender, registration dates), Medical History (Event dates, diagnosis, symptoms, risk factors, co-morbidities, referrals), Prescription (Rx dates, indication, therapeutic class, molecule, brand, dosage, posology, duration), Clinical Data (Height, weight, BP, life habits) and laboratory data.

Exposures: A patient will be identified as newly exposed when he/she has at least one dapagliflozin prescription recorded in the study database(s).

Outcomes: Outcomes include but are not limited to:

- Patient demographics: age, sex, country,
- Baseline history of type 2 diabetes,
- Baseline history of moderate or severe renal impairment,
- Concomitant medications at baseline and during dapagliflozin use.

Follow-up: Follow-up will begin on the date a patient is first prescribed dapagliflozin, which will represent the beginning of follow-up (i.e., "index date"). Follow-up will continue until the end of study or discontinuation of dapagliflozin (i.e., the final day of the days' supply for the last prescription for dapagliflozin). Follow-up will only be used to determine combination use with loop diuretics or pioglitazone. The baseline period is defined as the 12 months in the database preceding the index date.

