5 STUDY LIMITATIONS/STRENGTHS

5.1 Limitations Linked to Data Sources

As the study is based on fully anonymized real life, electronic medical records data, there are limitations inherent to the impossibility to link data from different databases and to get additional information from the physicians.

Data are collected by GPs: Even if some patients with type 2 diabetes mellitus may be treated exclusively by specialists, most of them will be treated by their GP at least for the treatment maintenance period. This study will not capture any use of dapagliflozin that is prescribed by specialists in Europe.

Data are collected in routine care: Cegedim's LPDs collect real life clinical practice information from the actual medical patients' records. A study specific CRF will not be used to collect supplemental information not entered in the medical records as part of the patient's routine clinical care. Also, as a non-interventional study, this protocol does not mandate any study specific visits or procedures.

Potential for missing data: No individual patient identifiers will be available. It is therefore impossible to query the physicians providing the data for any missing information.

¹ Dapagliflozin uptake was estimated from AZ forecasting models.

Data not recorded correctly in the databases: Recording of the indication of each prescribed treatment is mandatory in the Cegedim Software but the GP is free to enter any diagnosis and can for instance enter the reason of visit (*e.g.* flu) as indication for all treatments prescribed at the visit, and an oral antidiabetic drug may thus be recorded with an indication 'flu'.

Incomplete data: Clinical laboratory results are entered by the GPs whenever they deem these results relevant. The patient's renal function is therefore uncertain in the absence of recent creatinine. Similarly, weight may not be recorded by the physician at each consultation, which may impact the calculation of creatinine clearance calculation.

Absence of systematic recording of referrals to specialists: Except for the UK database, there is no systematic recording of referrals. If dapagliflozin is a secondary care initiation, this will not be recorded, leading to misclassification bias for newly initiated patients.

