5.2 Selection Bias

In order to more precisely describe the characteristics of European patients prescribed dapagliflozin (specifically baseline renal impairment), a minimum of 12 months (365 days) of medical history in the LPD is required prior to index date. Health care utilization patterns are best described when they include data from all potential prescribers of the drug. In this instance, the LPD data source does not capture prescriptions written in the specialist setting/hospitals; therefore, selection bias is possible if GPs prescribe dapagliflozin to a different patient population than a physician in a specialist setting. In the UK, the GP is a 'gatekeeper' of information for the patient and thus may be aware of and report health care visits or events taking place outside the GP setting. Thus, in the UK this selection bias may be less pronounced and UK THIN database can be used to estimate that selection bias in other databases.

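### The synopsis claim to represent national uptake, and the section 5.2 claim that UK data can estimate selection bias elsewhere, go beyond what GP-only records can show

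*Protocol*

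**What the plan says.** Two statements in the Protocol claim reach beyond general practice.

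- Synopsis, Study Population: "Dapagliflozin use will be representative of the uptake of dapagliflozin in the respective countries". The sentence carries no qualification.
- Section 5.2: the "UK THIN database can be used to estimate that selection bias in other databases".

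Other statements describe what the data hold.

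- Section 5.1: "This study will not capture any use of dapagliflozin that is prescribed by specialists in Europe".
- Section 5.2: "the LPD data source does not capture prescriptions written in the specialist setting/hospitals". For the UK it adds only that the GP "may be aware of and report health care visits or events taking place outside the GP setting", and that the bias may therefore be smaller there.
- Section 1.1: the database contains only general practitioners. Any French reimbursement is expected to be limited to specialist use, so no French users are expected.

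Section 4.1.1.2 sets out a related analysis: "To study patients that may be prescribed dapagliflozin in a specialist setting", the study will "primarily use the UK THIN database in which references to a specialist are recorded". Section 5.1 says referrals are not systematically recorded outside the UK, and continues: "If dapagliflozin is a secondary care initiation, this will not be recorded, leading to misclassification bias for newly initiated patients". Section 5.3 also lists specialist initiation as a source of error in identifying new users, and expects it to vary by country.

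**The concern.** The synopsis promises a property that the body of the Protocol says the data source lacks. Section 5.2 then offers the UK data as a way to measure the gap in other countries, although the UK data have the same gap.

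What is at stake is what the report may conclude. The study estimates proportions: aged 75 or older, renally impaired, taking loop diuretics or pioglitazone, without a diabetes code. If specialists prescribe to a different mix of patients, a proportion among GP-prescribed users differs from the national one. A reader who takes the synopsis at its word would read GP figures as national figures. A reader who takes section 5.2 at its word would expect a UK-derived allowance for the difference in the other five countries.

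**Working it through.** **1. The plan's own size figure.** The two claims contain no number. The only size figure is the forecast in Table 4.2-1, which is the annual number of oral antidiabetic drug users multiplied by the yearly uptake in Table 4.2-2, summed over years (the pooled row is used for Belgium).

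| Country | Annual users | Summed uptake | Product | Stated |
|---|---|---|---|---|
| France | 53,755 | 17.2% | 9,245.9 | 9,246 |
| UK | 48,620 | 5.6% | 2,722.7 | 2,723 |
| Italy | 29,025 | 9.4% | 2,728.3 | 2,728 |
| Germany | 38,710 | 10.0% | 3,871.0 | 3,871 |
| Belgium | 10,785 | 10.3% | 1,110.9 | 1,111 |
| Spain | 9,504 | 6.8% | 646.3 | 646 |
| Total | | | 20,325.1 | 20,325 |

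The forecast reproduces. France is 9,246 / 20,325 = 45.5% of it. Without France, 20,325 − 9,246 = 11,079 remain. The UK is 2,723 / 20,325 = 13.4%.

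**2. Representativeness.** On the Protocol's own account, the country with the largest forecast is expected to contribute no users, because use there would lie with specialists. If that happens, the cohort cannot represent French uptake. In the other countries it represents uptake only if specialist-only use is negligible or resembles GP use. The Protocol asserts neither, and section 5.2 treats a difference as possible.

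**3. What estimating the bias would require.** In a given country, let s be the share of users treated only by specialists, p_GP the proportion with a characteristic among GP-prescribed users, and p_S the same proportion among specialist-only users. Then

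p_all = (1 − s) × p_GP + s × p_S

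p_GP − p_all = s × (p_GP − p_S)

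GP prescribing records estimate p_GP. They contain neither s nor p_S, because a patient treated only by specialists has no prescription in the database and never enters the cohort. This is as true of the UK as elsewhere: the UK qualification in section 5.2 concerns visits and events, not prescriptions. A recorded referral shows that a patient was sent to a specialist, not that the specialist prescribed dapagliflozin.

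**4. Neither size nor sign is fixed.** Purely as an assumption, since none of these values is in the documents, take p_GP = 10%, s from 0.1 to 0.7 and p_S from 5% to 30%. At s = 0.7, p_all = 0.3 × 10% + 0.7 × 5% = 6.5% at one end, and 0.3 × 10% + 0.7 × 30% = 24% at the other. The GP data show 10% throughout.

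**5. Carrying a UK figure abroad.** Even if the UK values were known, the bias in another country depends on that country's own s and p_S. The Protocol gives reasons to expect differences: section 5.2 singles out the UK GP as gatekeeper, section 5.3 expects misclassification to vary by country, and section 1.1 describes France in effect as s = 1, where GP data carry no information.

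**6. What the UK data can show.** Section 5.1 expects most patients to be treated by their GP at least during maintenance. A specialist-started patient continued by a UK GP is therefore in the cohort and may have a recorded referral. The index date is the first prescription in the database (sections 3.1 and 3.4.2), so for such a patient some values counted as baseline may have been taken on treatment. A split by recorded referral probes this misclassification of new users. It does not observe specialist-only use.

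**The case against.** The strongest reply is that the limitation is openly disclosed. Sections 5.1 to 5.3 state that specialist prescriptions are missing, name the resulting selection bias and list specialist initiation as a source of misclassification. Section 1.1 is frank about France, and section 5.4 confines generalizability to patients meeting the entry criteria. The synopsis sentence may be meant as shorthand for the panel's representativeness of primary care physicians described in section 3.3, and section 5.2 says only that UK data can be used, without specifying an estimator.

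Much of this stands. Nothing is concealed, and the primary GP-based tables would not change. But disclosure does not reconcile the statements. A panel representative of primary care is not a cohort representative of a drug's uptake, and a hedged statement that a bias can be estimated is still wrong when the needed quantities are not in the data.

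A reader might go further and infer that the section 4.1.1.2 analysis is impossible, or that it claims to bound the bias. The text supports neither. It proposes to study patients who may be prescribed dapagliflozin in a specialist setting, and those continued by a GP are partly visible through UK referrals. Nor is it a fault that the Protocol does not define referral strata: section 4.1 leaves analysis detail to a SAP that is not at hand.

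**Conclusion.** The point holds for two statements: the synopsis sentence on representativeness and the section 5.2 sentence on estimating selection bias in other databases. Both contradict the Protocol's own description of the data source. Section 4.1.1.2 needs its scope stated, not removal.

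The bias cannot be sized from the documents. It would be wrong to infer that the GP figures understate use in older or renally impaired patients, because the direction depends on specialist-only patients, who are not observed. The 45.5% French share is a measure of how much of the forecast is affected, not of bias. It rests on a commercial forecast for 2012 to 2017 and on an expectation that section 1.1 says may change with reimbursement.

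It would also go too far to say that the regulator asked for these particular groups; section 1.1 attributes the study as a whole to a regulatory request to describe users in usual practice. The conclusion assumes only that sections 5.1 and 5.2 describe the databases correctly.

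**What to change.** 1. Synopsis, Study Population: replace the representativeness sentence with wording such as *Results describe dapagliflozin use prescribed by general practitioners in the panel practices, reported by country.*
2. Section 5.2: delete the statement that UK data can estimate selection bias in other databases. The remark that the bias may be less pronounced in the UK can stay as a qualitative comment.
3. Section 4.1.1.2: state that the UK analysis concerns GP-prescribed patients with a recorded specialist referral, some of whom may have been started by a specialist. Report the baseline results for UK initiators with and without a recorded referral as a sensitivity check on new-user misclassification. Say that referral is an imperfect proxy in both directions: a referred patient may have been started by the GP, and a patient without a recorded referral may have been started elsewhere. Interpret the comparison for the UK only, and not as a measure of specialist-only use. The window and specialties that define a referral can be set in the SAP.

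The cost is two wording changes and one stratified UK table from data the Protocol says are already recorded. The downside is a narrower stated scope and small strata, since the UK is forecast to supply only 2,723 users in total.
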